8.2.4. Chest Radiography

A PA CXR, interpreted and reported by a radiologist or pulmonologist, will be obtained as specified in the SoA of this master protocol (Section 1.3) and in the SoA of the relevant ISA, if applicable. The CXR films or images or a radiology report must be available to the investigator for review before the participant is randomized.

In addition to the PA CXR, a lateral CXR can also be obtained if, in the opinion of the investigator, a lateral view is indicated.

Note: Participants do not need to have a CXR at screening if, based on the judgment of the investigator, both of the following 2 conditions are met:

- the CXR was performed within 6 months before initial screening, and
- documentation of the CXR, read by a qualified radiologist or pulmonologist, is sufficient for pericardial and pleural effusion per EULAR/ACR 2019 classification criteria and for TB evaluation according to local standard of care.

Certain findings from CXR may be consistent with a condition that excludes a participant from the study; see Section 5.2.

Note: Results of a chest CT scan or other imaging study similar to a CXR may be substituted in place of the CXR as described above, in consultation with the sponsor's medical monitor.

8.2.5. Laboratory Tests

See Appendix 10.2 and the SoA (Section 1.3) for the clinical laboratory tests to be performed during the screening period of this master protocol. See the relevant ISA for clinical laboratory tests to be performed in treatment and posttreatment study periods.

All protocol-required laboratory assessments, as defined in the ISAs and in this master protocol, must be conducted in accordance with the SoAs, standard collection requirements, and applicable study laboratory manual.

If laboratory values from non-protocol specified laboratory assessments performed at an investigator-designated local laboratory require a change in participant management or are considered clinically significant by the investigator (for example, SAE or AE or dose modification), then report the information as an AE.

Reviewing and recording test results

The investigator must review the laboratory results, document this review, and report any clinically relevant changes occurring during the study as an AE. The laboratory results must be retained with source documents unless a Source Document Agreement or comparable document cites an electronic location that accommodates the expected retention duration. Clinically significant abnormal laboratory findings are those which are not associated with the underlying disease, unless judged by the investigator to be more severe than expected for the participant's condition.

Repeat testing after clinically significant abnormal findings

All laboratory tests with values considered clinically significantly abnormal during participation in the study, or within a time period equivalent to the maximum 5 half-lives of active interventions after the last dose of study intervention, should be repeated until the values return to normal or baseline or are no longer considered clinically significant by the investigator or medical monitor. If such values do not return to normal/baseline within a period of time judged reasonable by the investigator, the etiology should be identified and the sponsor notified.

Laboratory tests after hypersensitivity events

See the relevant ISA.

Allowance for additional laboratory testing

Additional tests may be performed at any time during the study as deemed necessary by the investigator or as required by local regulations.

8.2.5.1. Pregnancy Testing

Pregnancy testing (serum or urine) is to be performed for WOCBP and females with a history of tubal ligation. Participants who are pregnant will be discontinued from the study intervention (see Section 7.1).

Visits and times

Pregnancy testing (serum or urine) will be performed as specified in Appendix 10.2, in the SoA of this master protocol (Section 1.3), and in the relevant ISA. If the specified study visit includes administration of study intervention, the urine pregnancy test must be "negative" within 24 hours before dosing.

If a urine pregnancy test is not available, a local serum pregnancy test is an acceptable alternative.

Additional pregnancy testing (serum or urine) may be performed at additional time points at the discretion of the investigator or if this is required by local regulations.

If the urine pregnancy test is inconclusive at any visit, an additional serum pregnancy test should be collected.

Optional FSH testing

The participant's FSH level can be obtained during screening at the discretion of the investigator to assist in determining whether the participant meets the definition of *postmenopausal*. The FSH level can also be optionally obtained during the study to determine the participant's postmenopausal status (see Appendix 10.4).

8.2.6. Tuberculosis Testing and Monitoring

TB testing

During screening, all participants are to be assessed for risk factors, symptoms, and signs of TB with all of the following:

- Thorough history to determine the lifetime risk factors for TB infection, for TB progression, and for symptoms and/or signs of active TB, and
- Signs of previous or active TB by means of
 - Thorough physical examination for signs of active TB, including measurement of body temperature (Section 8.2.1) and assessment of peripheral lymph nodes, and
 - PA CXR interpreted and reported by radiologist or pulmonologist (Section 8.2.4).

All participants with no history of LTBI or active TB, and no history of positive Mantoux TST using PPD or positive *Mycobacterium tuberculosis* IGRA must have one of the following:

PPD TST

• The TST is performed by injecting 0.1 mL of tuberculin PPD into the inner surface of the forearm. The injection should be made with a tuberculin syringe, with the needle bevel facing upward. The TST is an intradermal injection. When placed correctly, the injection should produce a pale elevation of the skin (a wheal) 6 to 10 mm in diameter. Measure induration at site of intradermal injection 48 to 72 hours after intradermal injection. The test must be read during this window of time. The reaction should be measured in millimeters of induration (palpable, raised, hardened area or swelling). The reader should not measure erythema (redness). The diameter of the indurated area should be measured across the forearm (perpendicular to the long axis).

- An induration of 5 or more millimeters is considered positive in:
 - HIV-infected persons
 - A recent contact of a person with TB disease
 - Persons with fibrotic changes on chest radiograph consistent with prior TB
 - · Persons with organ transplants, and
 - Persons who are immunosuppressed for other reasons (for example, taking the equivalent of >15 mg/day of prednisone for 1 month or longer, or taking TNF-α antagonists)
- An induration of 10 or more millimeters is considered positive in all other potential clinical trial participants.
- Two-step testing (repeat TST from 1 to 3 weeks after the first TST) is recommended for certain participant groups, based on investigator judgment, including:
 - persons receiving immunosuppressant treatment
 - persons with a history of temporally remote increased risk of TB infection, and
 - persons for whom the first test is negative, as per local public health and/or professional medical society recommendations.
- IGRA for *M tuberculosis*. Ensure that specimen handling, transport, timing, and laboratory procedures meet all requirements per package insert.

Note: If the investigator suspects false positive IGRA results in a participant with no increased risk of TB infection during lifetime, and no evidence of prior or current TB on physical examination and/or on CXR interpreted by radiologist and/or pulmonologist, as well as with investigator assessment by history and physical examination, and CXR report documented in CRF, the investigator may discuss retesting with the sponsor's designated medical monitor.

Retesting

One retest is allowed for participants with an "indeterminate" QuantiFERON®-TB Gold assay or "borderline" T-SPOT®.TB assay. Participants with 2 indeterminate QuantiFERON-TB Gold assays or 2 borderline T-SPOT.TB assays will be excluded.

Rescreening after diagnosis and treatment of LTBI

Participants diagnosed with LTBI are excluded (Section 5.2) unless they are candidates for LTBI treatment, are treated for LTBI, and the following criteria are met:

- After receiving at least 4 weeks of appropriate LTBI therapy (as per WHO or the United States CDC guidelines), there is no evidence of hepatotoxicity (ALT/AST must remain ≤2 times ULN) or other treatment intolerance. In this case, the participant may be rescreened (Section 5.4.2) and is not excluded due to LTBI.
- The participant must continue and complete appropriate LTBI therapy in order to remain eligible to continue to receive study intervention (Section 7.1).

Monitoring during the study

For all participants, monitoring for TB is to be continuous throughout the study. At a minimum, each participant is to have the following documented at least every 3 months:

- Thorough history to determine any risk factors for TB infection and for TB progression, symptoms or signs of active TB, and
- Thorough physical examination for signs of active TB, including measurement of body temperature and assessment of peripheral lymph nodes.

8.2.7. Hepatitis B Testing and Monitoring

As specified in the SoA of this master protocol (Section 1.3), initial testing for HBV infection includes HBsAg and anti-HBc.

- If HBsAg is positive, the participant is excluded.
- If HBsAg is negative and anti-HBc is negative, the participant is not excluded.
- If HBsAg is negative and anti-HBc is positive, further testing for HBV DNA is required.
 - o If the screening HBV DNA is positive, the participant is excluded.
 - If the screening HBV DNA is negative, the participant is not excluded. Repeat testing for HBV DNA is required at least every 3 months during the study, as specified in the SoA of the relevant ISA.

Management of enrolled participants with detectable HBV DNA during the study

If HBV DNA is detected ("positive") during the study, the study intervention will be temporarily withheld or permanently discontinued and participants should receive appropriate follow-up medical care as described in this master protocol Sections 7.1 and 7.1.1.

8.2.8. Hepatitis C Testing

As specified in the SoA of this master protocol (Section 1.3), initial testing for HCV infection includes testing for anti-HCV.

- If anti-HCV is positive, a serum test for circulating HCV RNA is required.
- If HCV RNA test is negative, the participant is not excluded.
- If HCV RNA test is positive, the participant is excluded (see Section 5.2).

Participants who have had HCV infection and have been successfully treated, defined as a sustained virologic response (HCV RNA by PCR negative for at least 24 weeks following treatment completion) are not excluded on the basis of HCV as long as HCV RNA test is negative at screening.

If HCV RNA is detected during the study, the study intervention will be discontinued (Section 7.1), and the participant should receive appropriate follow-up medical care.

8.2.9. Hepatic Safety Monitoring

Close hepatic monitoring

Laboratory tests (Appendix 10.6), including ALT, AST, ALP, TBL, direct bilirubin, gamma-glutamyl transferase, and creatine kinase, should be repeated within 48 to 72 hours to confirm the abnormality and to determine if it is increasing or decreasing, if 1 or more of these conditions occur:

If a participant with baseline results of	develops the following elevations:
ALT or AST <1.5 times ULN	ALT or AST ≥3 times ULN
ALP <1.5 times ULN	ALP ≥2 times ULN
TBL <1.5 times ULN	TBL ≥2 times ULN (except for patients with Gilbert's syndrome)
ALT or AST ≥1.5 times ULN	ALT or AST ≥2 times baseline
ALP≥1.5 times ULN	ALP ≥2 times baseline

Abbreviations: ALP = alkaline phosphatase; ALT = alanine aminotransferase; AST = aspartate aminotransferase; TBL = total bilirubin; ULN = upper limit of normal.

If the abnormality persists or worsens, clinical and laboratory monitoring, and evaluation for possible causes of abnormal liver tests should be initiated by the investigator in consultation with the Lilly-designated medical monitor. At a minimum, this evaluation should include physical examination and a thorough medical history, including symptoms, recent illnesses (for example, heart failure, systemic infection, hypotension, or seizures), recent travel, history of concomitant medications (including over-the-counter), herbal and dietary supplements, history of alcohol drinking and other substance abuse.

Initially, monitoring of symptoms and hepatic biochemical tests should be done at a frequency of 1 to 3 times weekly, based on the participant's clinical condition and hepatic biochemical tests. Subsequently, the frequency of monitoring may be lowered to once every 1 to 2 weeks, if the participant's clinical condition and lab results stabilize. Monitoring of ALT, AST, ALP, and TBL should continue until levels normalize or return to approximate baseline levels.

Comprehensive hepatic evaluation

A comprehensive evaluation should be performed to search for possible causes of liver injury if 1 or more of these conditions occur:

If a participant with baseline results of	develops the following elevations:
ALT or AST <1.5 times ULN	ALT or AST ≥3 times ULN with hepatic signs/symptoms ^a or ALT or AST ≥5 times ULN
ALP <1.5 times ULN	ALP ≥3 times ULN
TBL <1.5 times ULN	TBL ≥2 times ULN (except for patients with Gilbert's syndrome)
ALT or AST≥1.5 times ULN	ALT or AST ≥2 times baseline with hepatic signs/symptoms ^a or ALT or AST ≥3 times baseline
ALP ≥1.5 times ULN	ALP ≥2 times baseline

Abbreviations: ALP = alkaline phosphatase; ALT = alanine aminotransferase; AST = aspartate aminotransferase; TBL = total bilirubin; ULN = upper limit of normal.

At a minimum, this evaluation should include physical examination and a thorough medical history, as outlined above, as well as tests for PT-INR; tests for viral hepatitis A, B, C, or E; tests for autoimmune hepatitis; and an abdominal imaging study (for example, ultrasound or CT scan).

Based on the participant's history and initial results, further testing should be considered in consultation with the Lilly-designated medical monitor, including tests for HDV, CMV, EBV, acetaminophen levels, acetaminophen protein adducts, urine toxicology screen, Wilson's disease, blood alcohol levels, urinary ethyl glucuronide, and blood phosphatidylethanol. Based on the circumstances and the investigator's assessment of the participant's clinical condition, the investigator should consider referring the participant for a hepatologist or gastroenterologist consultation, MRCP, ERCP, cardiac echocardiogram, or a liver biopsy.

8.2.9.1. Additional Hepatic Data Collection in Participants Who Have Abnormal Liver Tests During the Study

Additional hepatic safety data collection in hepatic safety CRFs should be performed for participants who meet 1 or more of the following 5 conditions:

- Elevation of serum ALT to ≥5 times ULN on 2 or more consecutive blood tests (if baseline ALT <1.5 times ULN)
 - o In participants with baseline ALT ≥1.5 times ULN, the threshold is ALT ≥3 times baseline on 2 or more consecutive tests.
- Elevated TBL to ≥ 2 times ULN (if baseline TBL <1.5 times ULN) (except for cases of known Gilbert's syndrome)

^a Hepatic signs/symptoms are severe fatigue, nausea, vomiting, right upper quadrant abdominal pain, fever, rash, and/or eosinophilia >5%.

- In participants with baseline TBL ≥1.5 times ULN, the threshold should be TBL ≥2 times baseline.
- Elevation of serum ALP to ≥2 times ULN on 2 or more consecutive blood tests (if baseline ALP <1.5 times ULN)
 - In participants with baseline ALP ≥1.5 times ULN, the threshold is ALP ≥2 times baseline on 2 or more consecutive blood tests.
- Hepatic event considered to be an SAE
- Discontinuation of study drug due to a hepatic event (Section 7.1)

Note: The interval between the 2 consecutive blood tests should be at least 2 days.

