
- [42] Have any of the following specific abnormalities on screening laboratory tests (Visit 1):
 - ALT or AST >2 times ULN
 - TBL ≥1.5 times ULN
 - hemoglobin <8.0 g/dL (<80.0 g/L)
 - total WBC <2500 cells/ μ L (<2.50 × 10³/ μ L or <2.50 GI/L)
 - neutropenia ANC <1000 cells/μL (<1.00 × 10³/μL or <1.00 GI/L)
 - lymphopenia ALC <500 cells / μ L (<0.50 × 10³/ μ L or <0.50 GI/L)
 - thrombocytopenia platelets $<50,000 \text{ cells/}\mu\text{L}$ ($<50 \times 10^3/\mu\text{L}$ or <50 GI/L)
 - eGFR (MDRD method) <45 mL/min/1.73 m² (FDA 2020).

Note: For repeat testing of screening laboratory tests, see Section 5.4.1.

- [43] Have known hypogammaglobulinemia or a screening (Visit 1) IgG level <565 mg/dL (<5.65 g/L).
- [44] Have other abnormal laboratory values at screening (Visit 1) which, in the opinion of the investigator, indicate unacceptable risk for the participant's safety in the study.
- [45] Have screening ECG abnormalities that, in the opinion of the investigator, are clinically significant and indicate an unacceptable risk for the participant's safety in the study.

Previous or concurrent clinical study experience

- [46] Have previously been randomized in any study investigating an intervention used in this study.
 - Note: Patients who received only placebo in a non-IMMA study (that is, not one of the ISAs of this master protocol) may be considered for enrollment if other study entry criteria are met.
 - See criterion [22] for patients who received at least 1 dose of investigational intervention in an ISA of this master protocol.
- [47] Are currently enrolled in any other clinical study involving an investigational product or any other type of medical research judged not to be scientifically or medically compatible with this study.

Other exclusions

- [48] Are largely or wholly incapacitated, permitting little or no self-care, such as being bedridden or confined to wheelchair.
- [49] Have donated more than a single unit of blood within 4 weeks before randomization (Visit 2) or intend to donate blood during the course of the study.
- [50] Have evidence of current or history within 1 year of any substance use disorder of any severity as defined by the DSM-V (APA 2013) in the opinion of the investigator, excepting disorders of nicotine or caffeine use.

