7.1. Discontinuation of Study Intervention

Continuing in the study after discontinuation of study intervention

A participant who prematurely discontinues dosing with study intervention is strongly encouraged to remain in the study for safety monitoring through the treatment period and posttreatment follow-up as per ISA requirements.

See this master protocol (Section 8) and the relevant ISA (Section 1.3 [SoA] and Section 8) for data to be collected at the time of discontinuation from the study intervention and for activities in the posttreatment follow-up period and for any further evaluations that need to be completed.

Possible reasons for discontinuation of study intervention

The following reasons for early **permanent** discontinuation of study intervention apply to any ISA conducted under this master protocol.

Note: For laboratory values that meet early permanent discontinuation thresholds, the study intervention should be discontinued unless, in the opinion of the investigator, the laboratory abnormality is due to intercurrent illness or another identified factor. After consultation with the sponsor's designated medical monitor, the participant may be able to continue receiving study intervention. Laboratory tests may be repeated within 1 week to confirm whether discontinuation criteria have been met. Furthermore, if study intervention is not discontinued because of intercurrent illness, the investigator must confirm that the laboratory value no longer meets early discontinuation thresholds after the resolution of the intercurrent illness or other identified factor.

Hepatic event or liver test abnormality

The study drug should be interrupted or discontinued if one or more of these conditions occur:

Elevation	Exception
ALT or AST >8 times ULN	54
ALT or AST >5 times ULN for more than 2 weeks	
ALT or AST >3 times ULN and either TBL >2 times ULN or INR >1.5	In participants with Gilbert's syndrome, doubling of direct bilirubin should be used for drug interruption/discontinuation decisions rather than TBL >2 times ULN.

Elevation	Exception
ALT or AST >3 times ULN with the appearance of fatigue, nausea, vomiting, right upper quadrant pain or tenderness, fever, rash, and/or eosinophilia (>5%)	
ALP >3 times ULN, when the source of increased ALP is the liver	

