Hepatocellular Drug-Induced Liver Injury Screening Plot (TBL vs ALT or AST)	Placebo-controlled treatment period
Hepatocellular Drug-Induced Liver Injury Screening Table	Placebo-controlled treatment period
Cholestatic Drug-Induced Liver Injury Screening Plot (TBL vs ALP)	Placebo-controlled treatment period
Cholestatic Drug-Induced Liver Injury Screening Table	Placebo-controlled treatment period

Abbreviations: ALP = alkaline phosphatase; ALT = alanine aminotransferase; AST = aspartate aminotransferase; GGT = gamma glutamyl transferase; TBL = total bilirubin; ULN = upper limit of normal.

Participant profiles will be created for participants meeting criteria for a comprehensive hepatic evaluation (as defined in the IMMA protocol) and are in Safety analysis set.

Participant profiles will include demographics, disposition, information collected on the hepatic safety CRFs (where applicable) and a display of study drug exposure, adverse events, medications, blood pressure, heart rate, and the liver -related measurements over time.

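### The Section 7.1 liver stopping criteria and the Section 8.2.9 work-up triggers use different scales and cross, so a participant can meet a liver stop without the specified 8.2.9 repeat, the comprehensive evaluation or an SAP profile

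*Protocol*

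**What the plan says.** **Stopping criteria (Protocol 7.1).** Study drug is to be interrupted or stopped on any of several liver conditions. Apart from an exception for Gilbert's syndrome, the liver-test limits are multiples of ULN whatever the baseline. Three of them are "ALT or AST >3 times ULN with the appearance of fatigue" or another listed symptom, "ALT or AST >3 times ULN and either TBL >2 times ULN or INR >1.5", and "ALP >3 times ULN, when the source of increased ALP is the liver". The others are ALT/AST above 8 times ULN, ALT/AST above 5 times ULN for over 2 weeks, and ALP above 2.5 times ULN with symptoms or with raised bilirubin.

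**Triggers (Protocol 8.2.9).** There are two tiers.
- Close monitoring: a panel whose named tests end with "gamma-glutamyl transferase, and creatine kinase, should be repeated within 48 to 72 hours". With baseline below 1.5 times ULN, it starts at ALT/AST of 3 times ULN or ALP of 2 times ULN. With a higher baseline, it starts at twice baseline.
- Comprehensive evaluation: with baseline below 1.5 times ULN, it starts at ALT/AST of 3 times ULN with symptoms, ALT/AST of 5 times ULN without, or ALP of 3 times ULN (no symptom limb). With a higher baseline, it starts at "ALT or AST ≥2 times baseline with hepatic signs/symptoms", at 3 times baseline for ALT/AST without symptoms, or at twice baseline for ALP.

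Footnote a begins "Hepatic signs/symptoms are severe fatigue, nausea, vomiting", whereas 7.1 lists fatigue without a severity qualifier.

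**Who can enter.** Criterion [42] in Section 5.2 excludes "ALT or AST >2 times ULN" and contains no ALP limit.

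**What is recorded and reported.** Section 8.2.9.1 opens the hepatic CRF on five conditions. One is discontinuation for a hepatic event; interruption is not among them. SAP 4.10.3.1 says "Participant profiles will be created for participants meeting criteria for a comprehensive hepatic evaluation".

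**The concern.** The participants for whom confirmation, a cause and a full record matter most are those who have met a stopping criterion. One would expect every 7.1 liver stop to lie inside the 8.2.9 triggers. Because one section counts from ULN and the other from baseline, and because the symptom wording differs, some stops fall outside. Those participants can be taken off drug without the timed repeat, the fixed cause search or an individual profile. Liver cases are then documented unevenly, and whether a case is documented depends on the participant's baseline.

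**Working it through.** The plan states no figure to reproduce, so the check applies the rules to each other. All values are multiples of ULN; b is baseline ALT/AST and p is baseline ALP. Analytes not mentioned are taken to be below their own triggers. Baseline is read as in SAP 4.3 (last value before first dose, usually Visit 2).

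**1. ALT/AST with symptoms, b of 1.5 or more.** The stop is >3. The repeat starts at 2b, and the comprehensive evaluation with symptoms also starts at 2b. Stop without either: 3 < ALT < 2b, which needs b > 1.5.

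**2. ALT/AST above 5 for over 2 weeks, no symptoms.** The comprehensive trigger is 3b. Stop without it: 5 < ALT < 3b, which needs b > 5/3 = 1.67. The repeat is triggered here, since 2b is at most 4.0.

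| b | 2b | Stop with symptoms, neither table | 3b | Sustained stop, no comprehensive evaluation |
|---|---|---|---|---|
| 1.5 | 3.0 | none | 4.5 | none |
| 1.6 | 3.2 | 3.0 to 3.2 | 4.8 | none |
| 1.8 | 3.6 | 3.0 to 3.6 | 5.4 | 5.0 to 5.4 |
| 1.9 | 3.8 | 3.0 to 3.8 | 5.7 | 5.0 to 5.7 |
| 2.0 | 4.0 | 3.0 to 4.0 | 6.0 | 5.0 to 6.0 |

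Example: b = 1.9, ALT 3.5, right upper quadrant pain. 3.5 > 3, so the stop is met. 3.5 < 3.8, so neither table is.

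**3. ALP, p = 2.0.** Both tables start at 2p = 4.0. ALP of hepatic source above 3 and below 4 is a stop with neither table. With symptoms the zone is above 2.5 and below 4.

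**4. Normal baselines (below 1.5).** The repeat is triggered in both cases below; the comprehensive evaluation is not.
- ALT/AST >3 to <5 with non-severe fatigue: a stop under 7.1, but not a symptom under footnote a.
- ALP >2.5 to <3 with symptoms: a stop, but the comprehensive ALP row starts at 3 and has no symptom limb.

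**5. INR limb.** PT-INR is a named minimum test only in the comprehensive evaluation. Without symptoms and with TBL below 2, that starts at ALT/AST 5 for a normal baseline. From >3 to <5, PT-INR is therefore not a named minimum. Close monitoring does cite Appendix 10.6, which lists PT-INR, but that appendix refers back to 8.2.9 for choosing tests. At b = 2.0 and ALT 3.5 close monitoring is not triggered, so the appendix is not reached by that route.

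**6. Where there is no gap.** ALT >3 with TBL >2 (baseline TBL below 1.5, no Gilbert's syndrome) meets both tables. So does ALT >8 with b up to 2.0.

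**7. Records.** In zones 1 to 3 the ratio-based CRF conditions in 8.2.9.1 are not met either (ALT below 3b, ALP below 2p), so an interruption alone does not open the hepatic CRF through them. In the normal-baseline ALP case, ALP of at least 2 on two consecutive tests can open it.

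**The case against.** The strongest reply is that much follow-up exists outside 8.2.9. Section 7.1 permits a repeat within a week. Section 8.2.5 asks for clinically significant abnormal values to be repeated. After a liver stop, drug may be resumed only once liver tests are back at baseline and a transient cause other than the drug has been found. Appendix 10.3 obliges investigators to arrange further evaluation of adverse events when medically indicated or requested. The ALP-alone stop applies only if the liver is the source, so some assessment must already have been made. Discontinuation for a hepatic event already opens the hepatic CRF.

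All of this stands, and it rules out some stronger readings:
- A reader might infer that these participants get no confirmatory test or work-up at all. The documents do not say so. What is missing is the 48-to-72-hour repeat (zones 1 and 3), the comprehensive evaluation and the profile. The first two safeguards above are optional or depend on judgement, and the resumption rule applies only if restarting is considered.
- A reader might infer that the INR criterion cannot be applied between 3 and 5 times ULN. That goes too far: the Appendix 10.6 reference can be read as including PT-INR, extra tests are always allowed, and on-treatment panels are in the ISA, which is not among the documents reviewed.
- A reader might infer that these cases vanish from the hepatic review. They do not. SAP Table 4.3 counts ALT/AST at 3 and 5 times ULN and ALP at 2 and 3 times ULN regardless of baseline, and the drug-induced liver injury plots and tables remain. Only the individual profile is lost.

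None of this removes the conflict between the thresholds. Section 7.1 applies to any ISA, so the master text should be coherent by itself.

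**Conclusion.** The contradiction holds. A participant eligible at screening can meet a 7.1 liver stop while meeting neither 8.2.9 table, and so fall outside the SAP profile rule. That complete gap needs a baseline ALT/AST above 1.5 times ULN, or a raised baseline ALP (1.5 times ULN or more for the stop with symptoms, above 1.5 for ALP alone). With baseline ALT/AST up to 2.0 it is at most one ULN wide. With normal baselines the loss is limited to the comprehensive evaluation and the profile, plus an ambiguity over PT-INR.

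These are widths of threshold zones, not counts of participants. The documents give no distribution of baseline liver tests; in an ISA of about 90 participants the number affected is unknown and probably small. The upper limit of 2.0 assumes baseline stays within the Visit 1 limit. Baseline is usually taken at Visit 2, so it could be higher and the zones wider.

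**What to change.** Reconcile Section 7.1, both 8.2.9 tables and footnote a, so that the relation between a liver stop and the follow-up it brings is deliberate and stated. This includes using one symptom wording and saying whether PT-INR from Appendix 10.6 belongs to the close-monitoring draw. Which thresholds, symptom wording and tests are right is for the sponsor's clinical team. Sending every stop to the comprehensive tier would also bring its imaging and serology, so that choice is theirs too.

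Two changes concern data and reporting only. Amend SAP 4.10.3.1 so that profiles also cover every participant whose drug was interrupted or discontinued under a 7.1 liver criterion. Align the discontinuation condition in 8.2.9.1 with 7.1 so that an interruption also opens the hepatic CRF.

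The cost of these two is one SAP sentence, one protocol wording change, and a few more profiles and hepatic CRFs. The cost of the clinical reconciliation depends on what the sponsor decides.
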